### **9.4.5. Analysis of PODCI Quality Outcome Data**

Changes from baseline in modified PODCI scores of subjects will be summarized descriptively based on available data at each assessment time point.

### **9.4.6. Pharmacokinetic Analyses**

Pamrevlumab concentrations and derived PK parameters (including Cmin, Cmax, AUCtau, and t1/2) will be summarized using descriptive statistics. Pharmacokinetic analysis will be performed using commercial software such as WinNonlin.

Descriptive statistics (number of subjects, mean, geometric mean, standard deviation, minimum, maximum, and coefficient of variation) will be presented for the PK parameters (1) in the overall population, (2) in subjects 12 to 16 years of age, and (3) in subjects older than 16 years.

Comparison of PK parameters between the age groups will be performed. Trough values, measured at several time points during the course of the study, will be compared to determine steady state and accumulation.

#### **9.4.7. Safety Analyses**

Safety analyses will include summary of adverse events, prior and concomitant medication use, measurements of laboratory tests, vital signs, and electrocardiograms (ECGs). In general, safety data will only be summarized descriptively and no inferential statistical procedures will be applied.

For data summarization, adverse events will be classified into standard terminology using a coding thesaurus (MedDRA), and reported by system organ class and preferred term.

Treatment-emergent adverse events will be tabulated to examine their frequency, severity, organ systems affected and relationship to study treatment. Deaths, SAEs, and AEs leading to study or treatment discontinuation, and infusion reactions will be listed or tabulated separately.

Clinically significant changes from baseline in vital signs, laboratory tests, and ECG will be identified. Shift tables will summarize changes in selected laboratory measures.

All safety analyses will be performed based on the Safety Population.

#### **9.5. Administrative Analyses**

In this open-label exploratory study, safety will be monitored on an ongoing basis.

The DMC will review all safety data, which may include available pharmacokinetic data, and pulmonary function tests.

## 10. DIRECT ACCESS TO SOURCE DOCUMENTS

Following site prequalification and/or initiation of the study site, periodic monitoring visits and site closeout visits will be made by FibroGen or its designee. The investigator must provide direct access to, and allocate sufficient space and time for, the monitor to inspect subject source records, CRFs, queries, collection of local laboratory normal ranges (if applicable), investigational product accountability records, and regulatory documents in accordance with GCP and the International Conference on Harmonisation (ICH) E6 guideline.

The purpose of trial monitoring is to verify the following:

- The rights and well-being of human subjects are protected.
- The reported data are accurate, complete, and verifiable from source documents
- All data are collected, tracked, and submitted by the site to FibroGen or designee, including unscheduled and missed assessments
- The reported data are reconciled across all data sources (e.g., laboratory, safety, IVRS [or IWRS], clinical databases).
- The conduct of the trial is in compliance with the currently approved protocol/amendment(s), with GCP, and with the applicable regulatory requirement(s).

The investigator must also permit the U.S. FDA or other applicable regulatory authorities to inspect facilities and records pertaining to this study if so requested. If the investigator is notified of an inspection pertaining to this study by the U.S. FDA or other applicable regulatory authorities, the investigator must notify FibroGen immediately.

## **11. QUALITY CONTROL AND QUALITY ASSURANCE**

### **11.1. Data Quality Assurance**

The following steps will be taken to ensure that the study is conducted by the study site in compliance with the study protocol, GCP, and other applicable regulatory requirements:

- Investigator meeting and/or investigator site initiation
- Routine study site monitoring
- Documented study and system training
- CRF and query review against source documents

### **11.2. Audit and Inspection**

Authorized representatives of the sponsor, a regulatory authority, an independent ethics committee (IEC) or an institutional review board (IRB) may visit the investigator site to perform audits or inspections, including source data verification. The Investigator will allow the sponsor auditor, regulatory authority or ethics committee representative to inspect the drug storage area, study drug stocks, drug accountability records, subject charts and study source documents, and other records relative to study conduct.

The purpose of an audit or inspection is to systematically and independently examine all study-related activities and documents to determine whether these activities were conducted, and data were recorded, analyzed, and accurately reported according to the protocol, GCP guidelines of the International Conference on Harmonization, and any applicable regulatory requirements.

The investigator should contact the sponsor immediately if contacted by a regulatory agency about an inspection.

## **12. ETHICS**

### **12.1. Ethical Considerations**

The study will be conducted in accordance with U.S. Food and Drug Administration (FDA) regulations, the International Conference on Harmonisation (ICH) E6 Guideline for Good Clinical Practice (GCP), the Declaration of Helsinki, any other applicable regulatory requirements, and Institutional Review Board (IRB) or independent ethics committee (IEC) requirements.

### **12.2. Communication with the Institutional Review Board or Independent Ethics Committee**

This protocol, the Informed Consent Form, the Investigator's Brochure, and any information to be given to the subject must be submitted to a properly constituted IRB/IEC by the investigator for review and approved by the IRB/IEC before the study is initiated and before any investigational product is shipped to the investigator. In addition, any subject recruitment materials must be approved by the IRB/IEC before the material is used for subject recruitment.

The investigator is responsible for obtaining reapproval by the IRB/IEC annually or more frequently in accordance with the regulatory requirements and policies and procedures established by the IRB/IEC. Copies of the investigator's annual report and other required report to the IRB/IEC and copies of the IRB/IEC continuance of approval must be furnished to FibroGen. A copy of the signed form FDA 1572 must also accompany the above approval letter provided to FibroGen.

Investigators are also responsible for promptly informing the IRB/IEC of any protocol changes or amendments, changes to the Investigator's Brochure, and other safety-related communications from FibroGen. Written documentation of IRB approval must be received before the amendment is implemented.

Investigators must also enter the names of the staff that are involved in the study on the Delegation of the Authority form and sign the form (including their responsibilities). This form must be updated when responsibilities of the staff change.

### **12.3. Informed Consent Form**

No study procedure may be implemented prior to obtaining a signed, written Informed Consent (ICF) and/or Assent Form from the subject or written Informed Consent Form signed by the subject's legally authorized representative, as applicable. IRB review and approval are required for the ICF. The final IRB/IEC approved ICF must be provided to FibroGen for regulatory purposes.

If there are any changes to the Sample ICF during the subjects' participation in the study, the revised ICF must receive the IRB/IEC's written approval before use and subjects must be re-consented to the revised version of the ICF.

Guidance for Clinical Teams: For studies conducted in the United States, each subject must provide his or her consent for the use and disclosure of personal health information under the U.S. Health Insurance Portability and Accountability Act (HIPAA) regulations by signing a

HIPAA Authorization Form. The HIPAA Authorization Form may be part of the ICF or may be a separate document. IRB review may or may not be required for the HIPAA Authorization Form according to study site policies.

#### **12.4. Subject Confidentiality**

Release of research results should preserve the privacy of medical information and must be carried out in accordance with Department of Health and Human Services Standards for Privacy of Individually Identifiable Health information, 45 CFR Parts 160 and 164, and HIPAA.

Subject medical information obtained as part of this study is confidential and may only be disclosed to third parties as permitted by the Informed Consent and HIPAA Authorization Form or separate authorization to use and disclose personal health information signed by the subject, or unless permitted or required by law. The subject may request in writing that medical information be given to his/her personal physician.

## **13. DATA HANDLING AND RECORD KEEPING**

### **13.1. Source Documents**

Source documents are original documents, data, and records that are relevant to the clinical study. The investigator will prepare and maintain adequate and accurate source documents. These documents are designed to record all observations and other pertinent data for each subject enrolled in this clinical study. Source documents must be adequate to reconstruct all data transcribed onto the CRFs/eCRFs and resolved queries.

### **13.2. Data Collection, Handling, and Verification**

All required data will either be entered onto CRFs/eCRFs by authorized site personnel or will be provided as a data transfer from authorized service providers (such as laboratory results from a central laboratory). Data will be entered or uploaded into a validated, clinical database compliant with 21 CFR Part 11 regulations. The database will be a secured, password-protected system with a full audit trail.

All subject data will be reviewed by Sponsor and/or designee. Data that appear inconsistent, incomplete or inaccurate will be queried for site clarification.

Medical history, adverse events and medications will be coded using industry standard dictionaries (e.g., MedDRA and World Health Organization Drug [WHODrug]) Dictionary.

The investigator is responsible for reviewing, verifying, and approving all subject data, i.e., CRFs and queries prior to study completion, ensuring that all data is verifiable with source documents.

#### **14. PUBLICATION POLICY**

A detailed explanation of FibroGen's publication policy is described in the Clinical Trial Agreement.

**16. APPENDICES**

## APPENDIX 1. SCHEDULE OF ASSESSMENTS: SCREENING PERIOD THROUGH WEEK 26

Assessment a	Screening Period (4 Weeks)	Treatment Period (Weeks)												
		Day 0	2	4	6	8	10	12	14	16	18	20	22	24
Informed Consent & Assent	X													
Inclusion/ Exclusion	X													
Demographics	X													
Medical History	X													
Clinical laboratory assessments b,1	X			X		X		X						X
Vital Signs c	X	X	X	X	X	X	X	X	X	X	X	X	X	X
Weight/Height d	X							X						X
Electrocardiogram	X													
Physical Examination e	X	X						X						X
Muscle function tests f	X	X						X						X
Pulmonary function tests g	X	X						X						X
Cardiac MRI i	X i													
Muscle MRI i	X i													
Specialty labs h		X	X											X
Pamrevlumab infusion		X	X	X	X	X	X	X	X	X	X	X	X	X
Adverse Events & Concomitant	X	X	X	X	X	X	X	X	X	X	X	X	X	X
PODCI Quality Outcome Questionnaire		X												X

Abbreviations: MRI, magnetic resonance imaging; PODCI, Pediatrics Outcomes Data Collection Instrument

- a. See [Section 7](#) for details on approved windows, assessments and dosing.
- b. Safety labs: See [Section 7.2.7.1](#). Central labs are required at visits noted in this table.
- c. Vital signs (pulse, respiration, sitting BP, temperature) to be collected at every visit, and pre-infusion, within 15 minutes of completion, and within 15 minutes of completing observation period.
- d. Weight and height (estimated from ulna length) to be measured at screening and every 3 months thereafter.
- e. Physical exam to include assessment of subject's ventilation use. A complete exam is required at screening. Other exams may be disease specific or problem oriented.
- f. Muscle function tests (MFT): Brooke Scale, Performance of Upper Limb, Pinch Test, and Grip Test. MFTs will be performed during the screening period. MFTs will be repeated on Day 0 (start of dosing) or at any time up to and including the Week 2 visit. The results from both time points will be used to establish baseline values.
- g. Pulmonary function tests (PFTs): forced vital capacity, forced expiratory volume in 1 second, maximal inspiratory pressure, maximum expiratory pressure, peak expiratory flow rate, peak cough flow. PFTs will be performed during the screening period. PFTs will be repeated on Day 0 (start of dosing) or at any time up to and including the Week 2 visit. The results from both time points will be used to establish baseline values.
- h. See [Appendix 5](#) for pharmacokinetic/human antihuman antibody/connective tissue growth factor and Exploratory Sample collection details.
- i. Baseline muscle MRI may be conducted during the screening period or up to Week 4 dosing visit. Local safety labs are required prior to the MRIs, and must include hematocrit.

## APPENDIX 2. SCHEDULE OF ASSESSMENTS: WEEK 28 THROUGH WEEK 58

Assessment a	Treatment Period (Weeks)													
	28	30	32	34	36	38	40	42	44	46	48	50	52	54,56, 58
Clinical laboratory assessments b,i					X						X			
Vital Signs c	X	X	X	X	X	X	X	X	X	X	X	X	X	X
Weight/Height d					X						X			
Electrocardiogram												X		
Physical Examination e					X						X			
Muscle function tests f					X						X			
Pulmonary function tests g					X						X			
Cardiac MRI i													X	
Muscle MRI i													X	
Specialty labs h														X
Pamrevlumab infusion	X	X	X	X	X	X	X	X	X	X	X	X	X	X
Adverse Events & Concomitant Medications	X	X	X	X	X	X	X	X	X	X	X	X	X	X
PODCI Quality Outcome Questionnaire													X	

Abbreviations: MRI, magnetic resonance imaging; PODCI, Pediatrics Outcomes Data Collection Instrument

- See [Section 7](#) for details on approved windows, assessments and dosing.
- Safety labs: See [Section 7.2.7.1](#). Central labs are required at visits noted in this table.
- Vital signs (pulse, respiration, sitting blood pressure, and temperature) to be collected at every visit, and pre-infusion, within 15 minutes of infusion completion and within 15 minutes of completing the observation period.
- Weight and height (estimated from ulna length) to be measured at screening and approximately every 3 months thereafter.
- Physical exam to include assessment of subject's ventilation use. A complete exam is required at Week 48. Other exams may be disease specific or problem oriented.
- Muscle function tests: Brooke Scale, Performance of Upper Limb, Pinch Strength Test, and Grip Test.
- Pulmonary Function Tests (PFTs): forced vital capacity, forced expiratory volume in 1 second, maximal inspiratory pressure, maximum expiratory pressure, peak expiratory flow rate, peak cough flow.
- See [Appendix 5](#) for pharmacokinetic/human antihuman antibody/connective tissue growth factor and Exploratory Sample collection details.
- Local safety labs are required prior to the MRIs and must include hematocrit.

### APPENDIX 3. SCHEDULE OF ASSESSMENTS: WEEK 60 THROUGH WEEK 104

Assessment a	Treatment Period (Weeks)								
	60	62,64, 66,68,70	72	74,76, 78,80,82	84	86,88,90 ,92,94	96	98,100,102	104
Clinical laboratory assessments b,1	X		X		X		X		
Vital Signs c	X	X	X	X	X	X	X	X	X
Weight/Height d	X		X		X		X		
Electrocardiogram									X
Physical Examination e	X		X		X				X
Muscle function tests f	X		X		X				X
Pulmonary function tests g	X		X		X				X
Cardiac MRI i									X
Muscle MRI i									X
Specialty labs h									X
Pamrevlumab infusion	X	X	X	X	X	X	X	X	X
Adverse Events & Concomitant Medications	X	X	X	X	X	X	X	X	X
PODCI Quality Outcome Questionnaire									X

Abbreviations: MRI, magnetic resonance imaging; PODCI, Pediatrics Outcomes Data Collection Instrument

- See [Section 7](#) for details on approved windows, assessments and dosing.
- Safety labs: See [Section 7.2.7.1](#). Central labs are required at visits noted in this table.
- Vital signs (pulse, respiration, sitting blood pressure, and temperature) to be collected at every visit, and pre-infusion, within 15 minutes of infusion completion and within 15 minutes of completing the observation period.
- Weight and height (estimated from ulna length) to be measured in screening and approximately every 3 months thereafter.
- Physical exam to include assessment of subject's ventilation use. A complete exam is required at Week 104. Other exams may be disease specific or problem oriented.
- Muscle function tests: Brooke Scale, Performance of Upper Limb, Pinch Strength Test, and Grip Test.
- Pulmonary Function Tests (PFTs): forced vital capacity, forced expiratory volume in 1 second, maximal inspiratory pressure, maximum expiratory pressure, peak expiratory flow rate, peak cough flow.
- See [Appendix 5](#) for pharmacokinetic/human antihuman antibody/connective tissue growth factor and Exploratory Sample collection details.
- Local safety labs required prior to the MRIs and must include hematocrit.

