### **TREATMENTS**

#### **Pamrevlumab Dose, and Mode of Administration**

Each subject will receive pamrevlumab (35 mg/kg, every 2 weeks) for a minimum of 104 weeks and will transition onto the OLE within 2-3 infusions of the approval of the amendment for up to an additional 208 weeks. The dose of pamrevlumab (35 mg/kg) for the first infusion should be based on body weight obtained during screening. Dose will be adjusted based on body weight taken approximately every 3 months thereafter.

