#### 6.1.4. Preparation of Dose for Administration

The dose of pamrevlumab (35 mg/kg) for the first infusion should be based on body weight obtained during screening. Dose will be adjusted based on body weight taken every 3 months thereafter. Pamrevlumab may be administered undiluted or, for convenience of infusion, may be diluted with 0.9% Sodium Chloride Injection according to the Dose Preparation Instructions in the Study Reference Investigational Product (IP) Manual.

Pamrevlumab will be administered as soon as possible after release from the site's pharmacy and within 48 hours of preparation and within 6 hours if left at room temperature after preparation. Pamrevlumab will be administered by IV infusion, using an infusion set with a sterile, nonpyrogenic, low-protein-binding in-line filter (0.2-micron pore size).

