## 6. OLE Schedule of Assessments: EX – Day 0 through Ex – week 210/EOS/ET

	Treatment Period a					Follow Up Period	
	Day 0 b	Q2 WEEKS: ALL VISITS through Week 206	Q12 weeks through Week 204 (Wk 12, 24, 36, etc.)	Q24 Weeks (Wk 24, 48, 72, etc.)	Q52 weeks through Week 156 (Wk 52, 104, 156, 208 r /EOT)	Wk 210/ EOS/ET p	Final Safety phone call 60 Days (+3 days) after last treatment
Informed Consent & Assent	x						
Eligibility Assessment	x						
Vital Signs c	x	x	x	x	x	x	
Chemistry & Hematology				x		x	
PFT / Height (ulna length) f,h,i				x		x q	
Muscle Function Tests f,g			x	x		x q	
Physical Examination k				x		x	
Weight j	x		x	x			
Weight Based Dose Adjustment j	x		x	x			
Cardiac MRI d,e,f					x	x q	
Specialty Labs o	x					x	
Pamrevlumab Infusion l	x	x	x	x	x		
AEs / SAEs m	x	x	x	x	x	x	x
Concomitant Medications n	x	x	x	x	x	x	x

Abbreviations: AE = adverse event; ECG = electrocardiogram; ET= Early Termination; ICF = Informed Consent Form; PFTs = Pulmonary Function Test;

a.) Visit window of  $\pm$  3 days starting at Week 2.

b.) Day 0 to be conducted simultaneously with, or within 7 days after the parent study EOT visit.

c.) Vital signs (pulse, respiration, sitting BP, temperature) to be collected at every visit: pre-infusion, and within 15 minutes of completion, and within 15 minutes of completing the observation period.

d.) Local safety labs are required prior to MRIs and must include hematocrit.

e.) Cardiac MRI may be performed within  $\pm$ 2 weeks of the specified visit

f.) PFTs, MFTs, and MRI do not require repetition if performed within 4 weeks.

- g.) For Non-ambulatory subjects only: Muscle Function Tests (MFTs): Performance of Upper Limb, and Grip Test.
- h.) Pulmonary Function Tests (PFTs): forced vital capacity, forced expiratory volume in 1 second, peak expiratory flow rate.
- i.) Height will be measured at each PFT interval using ulna length to approximate standing height until subject reaches adult height. Adult height will be carried forward.
- j.) Weight will be measured every 12 weeks to determine dose for the subsequent 12-week interval. Weight is collected during the dose adjustment visit or up to two weeks in advance.
- k.) Full physical exam including chest auscultation

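### Weight and height are scheduled at Week 96 and not again until Week 116, against a roughly 3-monthly dose-weight rule, and no height is scheduled at the Week 104 primary-endpoint lung function visit

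*Protocol*

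**What the plan says.** **Dose weight.** Protocol 6.1.4 states: "Dose will be adjusted based on body weight taken every 3 months thereafter". The synopsis, under dose and mode of administration, is looser: "Dose will be adjusted based on body weight taken approximately every 3 months thereafter". The Appendix 1 footnote reads "Weight and height (estimated from ulna length) to be measured at screening and every 3 months thereafter"; the footnotes to Appendices 2 to 4 add *approximately*, as in "Weight and height (estimated from ulna length) to be measured in screening and approximately every 3 months thereafter".

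**The grids.** The Weight/Height row is marked at screening and Weeks 12 and 24 (Appendix 1), 36 and 48 (Appendix 2), 60, 72, 84 and 96 (Appendix 3), and 116, 128, 140, 152, 168, 180, 192 and 204 (Appendix 4). The pulmonary function row follows the same weeks, except that the last test of each later cycle falls at Week 104, 156 or 208 instead of Week 96, 152 or 204.

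**Other sources of height or weight.** Section 7.2.6 defines the all-visit vital signs as pulse, respiration, blood pressure and temperature. Only the screening text in 7.1.1 puts weight and height among vital signs.

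**The extension.** Appendix 6 combines lung function and height in one row and states: "Height will be measured at each PFT interval using ulna length to approximate standing height until subject reaches adult height". Weight, but not height, is marked at OLE Day 0.

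**The concern.** Two things follow from the same rows.

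First, a site cannot follow both the 3-month text and the printed grid between Weeks 96 and 116. On the grid alone, up to ten infusions are given on one body weight.

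Second, percent predicted FVC divides measured FVC by a value predicted from height, among other things. The study enrols from age 12, so some subjects may still be growing. An out-of-date, shorter height makes predicted FVC too low and percent predicted FVC too high. At Week 104 this makes the decline look smaller, which favours clearing the -5% bound, and a single-arm trial has no control group in which the error would cancel. The visit without a height is the one that closes the primary endpoint, and Week 156 closes the exploratory one.

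**Working it through.** **1. The plan's own interval.** Three months is 3 × 30.4375 / 7 = 13.04 weeks. From Week 12 to Week 96 every interval between Weight/Height marks is 12 weeks, which agrees with the rule.

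**2. Where it departs.**

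| From | To | Gap |
|---|---|---|
| Week 96 | Week 116 | 20 weeks = 140 days = 4.6 months |
| Week 152 | Week 168 | 16 weeks = 112 days = 3.7 months |

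Infusions are every 2 weeks. Weeks 96 to 114 give (114 − 96)/2 + 1 = 10 infusions on the Week 96 weight, assuming the Week 116 dose uses the Week 116 weight. A 12-week cycle gives 6. The infusions at Weeks 110, 112 and 114 fall more than 13.04 weeks after the weight.

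**3. Dose arithmetic.** The documents give no weight gain; assume 4–8 kg/year from 60 kg. The shortfall from nominal mg/kg at lag *L* weeks is (gain × L/52) / (60 + gain × L/52).
- Week 114, L = 18: 1.385/61.385 = 2.3% to 2.769/62.769 = 4.4%.
- Last dose of a 12-week cycle, L = 10: 0.769/60.769 = 1.3% to 1.538/61.538 = 2.5%.

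**4. Post-baseline lung function visits without a same-visit height.** Week 104 (last height 8 weeks earlier), Week 156 (4 weeks) and Week 208 (4 weeks). Weeks 12–84, 116–140 and 168–192 all have one.

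**5. Height arithmetic, only if the Week 96 height is carried forward.** Assumptions, none from the documents: height 155 cm, growth *g* = 0–6 cm/year, percent predicted FVC 60, predicted FVC proportional to height to the power *p* = 2–2.7. Overstatement = 60 × [((155 + g × 8/52)/155)^p − 1].
- g = 0: 0.
- g = 2, p = 2: 60 × [(155.308/155)^2 − 1] = 0.24.
- g = 6, p = 2.7: 60 × [(155.923/155)^2.7 − 1] = 0.97.

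The range is therefore 0 to about 1.0 point at Week 104.

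**6. Per year.** This depends on the estimator, which the protocol leaves to a main-study SAP that was not supplied.
- Two-year change divided by 2: 0 to 0.97/2 = 0.48 points/year.
- Least-squares slope over Weeks 0, 12, …, 84, 104: mean time 440/9 = 48.89 weeks; sum of squares 30,976 − 440²/9 = 9,464.9; weight on Week 104 = (104 − 48.89)/9,464.9 × 52 = 0.303 per year. Result: 0 to 0.97 × 0.303 = 0.29 points/year.

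**7. Baseline offset.** Height is marked at screening but not Day 0, and baseline uses lung function from both. If the screening height was taken 4 weeks before Day 0, the largest error in the Day 0 value is 60 × [((155 + 6 × 4/52)/155)^2.7 − 1] = 0.48 points. Averaged with a screening value that has no lag, it is 0.24. The top of the Week 104 range would fall from 0.97 to about 0.73. The documents do not say how the two values are combined.

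**8. Scale.** The design difference is −2 − (−5) = 3 points, with an assumed SD of 5.

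**The case against.** The case for leaving this alone has real content.

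- **The rule is approximate.** Four of the places that state it say so. That arguably covers the 16-week gap. It does not plausibly cover 20 weeks, and 6.1.4 has no such qualifier.
- **Few subjects may be affected on dosing.** Anyone who enters the OLE at Week 104 is weighed at OLE Day 0. This stands. A reader might infer that all subjects were dosed on a 20-week-old weight, but the documents do not support that. Nor is any dose given on a 20-week-old weight: the oldest is 18 weeks, at Week 114.
- **Nothing says the Week 96 height is used.** A reader might infer that the primary Week 104 value rests on an 8-week-old height. No supplied passage says so; test conduct is referred to the Study Reference Manual, and the main-study SAP is not among the documents. The bias is therefore conditional.
- **No main-study rule requires same-visit height.** Also correct. Section 7.1.2 lets an inadequate test be repeated by the next dosing visit, so exact pairing was never guaranteed. The OLE rule shows that the sponsor considers the pairing relevant, but it does not bind the main study.
- **The effect is small.** The assumed 8-week growth is at most 0.9 cm, with height itself estimated from ulna length. Subjects at adult height contribute nothing.
- **The data are in.** The SAP Addendum's introduction reports database lock and a completed interim study report, so a schedule change cannot recover Week 104 heights.

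The last point limits the fix without removing it, because the sensitivity analysis is still possible. The OLE SAP also analyses change from the main-study baseline (section 9.2), and its natural-history comparison (section 9.2.4) uses main-study data.

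**Conclusion.** The point holds in two limited parts.

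*Dose weight:* the 20-week gap from Week 96 to Week 116 contradicts the 3-month text, for subjects who remain in the main study past Week 104. On assumed gains of 4–8 kg/year at 60 kg, the Week 114 dose would be 2.3–4.4% below nominal, against 1.3–2.5% at the end of an ordinary 12-week cycle. The 16-week gap is not a clear conflict.

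*Height:* the schedule omits height at the primary-endpoint visit and at Weeks 156 and 208, and the documents do not say which height is used. This is a gap in the plan and not a breach of a main-study rule. If the Week 96 height is carried forward, the error at Week 104 is 0 to about 1.0 point, or 0–0.5 points/year (simple change) or 0–0.3 (slope), before any baseline offset. It is modest against a 3-point design difference, but it runs one way, towards meeting the criterion. The tick positions are certain. The sizes rest on the growth, weight and prediction assumptions above.

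**What to change.** 1. Measure height by ulna length at the Week 104, 156 and 208/EOT lung function visits, and state that percent predicted FVC uses the height from the same visit. The cost is a few minutes at visits subjects already attend, plus a table correction. It cannot restore heights missed before database lock.
2. State which height was used for Week 104. Where none was taken at that visit, add a sensitivity analysis of the primary endpoint with height interpolated by date between Week 96 and the next measured height. With Week 116 this is H96 + (8/20) × (H116 − H96); for a subject who entered the OLE, use the first OLE lung function visit. The cost is one additional analysis on data already held.
3. Reconcile the dose-weight text in the synopsis and 6.1.4, and the schedule footnotes, with the Weight/Height rows of Appendices 3 and 4. Which dose-weight rule applies is for the sponsor to decide. The cost is a text or table correction.
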